1.2 Sample Size

For the primary efficacy endpoint of stable vision (ie, patients who lose fewer than 15 letters in BCVA from baseline) at Week 52, a sample size of 240 patients in each treatment group will provide approximately 95% power with a 2-sided alpha level of 0.05 to demonstrate non-inferiority of an abicipar group versus ranibizumab with a non-inferiority margin of 10%. This calculation is based on the assumption of a 90% response rate for both groups. With an anticipated dropout rate of approximately 20% during a 52-week period, a total of 900 patients will be enrolled so that approximately 720 patients (240 per group) will complete 52 weeks as required for the primary endpoint evaluation.

1.3 Database Lock and Procedures of Maintaining Masking

The study will be unmasked to a restricted group for the primary analysis following the Week 52 database lock. Access to randomization codes and unmasked information will be strictly limited to team members who will be working on data analysis, study report completion, and submission-related documents. To maintain the integrity of the ongoing study, Allergan personnel who become unmasked after the Week 52 database lock will not participate in any masked activities during the remaining part of the study until after the final database lock at study completion. In particular, the unmasked study statistician(s) and programmer(s) will no longer be involved in any ongoing study conduct or data review activities. Other statisticians and programmers, who are still masked to study treatment, will assume these responsibilities until study completion.

2. Analysis Populations and Data Conventions

2.1 Analysis Populations

The following 3 populations will be used for statistical analysis: intent-to-treat (ITT), perprotocol (PP), and safety.

The ITT population includes all randomized patients. The ITT population will be used for all efficacy analyses.

The PP population includes all randomized and treated patients who do not have protocol deviations that impact the primary efficacy variable. The PP population will be used for analyses of the primary and secondary efficacy variables. Primary considerations for PP definition include treatment compliance that would represent the intended regimen adequately.

Specifically, the PP population will include patients who

- 1. Received at least 9 study treatments (including sham) and attended at least 9 scheduled monthly visits during the first year (before the Week 52 visit), and;
- 2. Had not missed 3 or more consecutive study treatments (including sham) before the 9th study treatment, and;

3. Did not have any major protocol deviations that impacted efficacy outcomes prior to the Week 52 visit

The PP population will also include patients who discontinued from the study as a result of treatment failure without a major deviation prior to Week 52 that impacted efficacy outcomes (even if they met criteria #1 or #2 above). Patients who escaped to standard of care by meeting the protocol criteria before Week 52 and study exit are considered as treatment failures. Final determination of the PP population will be made based on masked review of the data. Detailed specification will be documented separately prior to the primary database lock.

The safety population includes all treated patients and will be used for all safety analyses.

Analyses for ITT and PP populations will be based on randomized treatment group, whereas analyses for safety populations will be as treated, ie, based on the actual treatment that the patient received.

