Abicipar pegol (hereafter referred to as abicipar) was in-licensed from Molecular Partners (MP). The drug substance (abicipar-1) was evaluated in 2 phase 1 studies; one in patients with neovascular AMD, and one in patients with diabetic macular edema.

These data support the proposed dosing regimens of both abicipar treatment arms in the phase 3 study. These abicipar treatment regimens afford the possibility to reduce the treatment burden of the number of intravitreal injections (8 or 6 abicipar intravitreal injections in Year 1 for the 2Q8 and 2Q12 abicipar arms, respectively, versus 13 for the ranibizumab arm), while maintaining the efficacy of an anti-VEGF therapy, including 3 initial doses followed by 8- or 12-week dosing intervals to assess the efficacy and safety of abicipar in a phase 3 study.

Approval Date: 10-Apr-2018

For further information, please refer to the Investigator's Brochure for abicipar.

[figure not shown]
The purpose of this study is to evaluate the safety and efficacy of abicipar (2 mg), compared to 0.5 mg ranibizumab in treatment-naïve patients with neovascular AMD.

2. Study Objectives and Clinical Hypotheses

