5.6.1 Treatment Regimen Adjustments

If the study eye develops a treatment-related adverse event at any time during the study, treatment dose may be temporarily held and the reason for dose holding will be recorded on the eCRF.

[figure not shown]
The treatment regimen will be adjusted based on the following criteria:

[figure not shown]
The investigator may hold or discontinue study treatment for other safety reasons at his/her discretion.

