7.3 Methods of Analysis

7.3.1 Primary Efficacy Analyses

The primary efficacy endpoint will be the proportion of patients with stable vision (ie, patients who lose fewer than 15 letters in BCVA from baseline) at week 52. The difference in the proportion between each abicipar arm and ranibizumab (abicipar group minus ranibizumab group) and the corresponding 2-sided 95.1% confidence interval (CI) for non-inferiority testing will be constructed based on Cochran-Mantel-Haenszel (CMH) method with the baseline BCVA stratification factor (≤ 55 ETDRS letters versus > 55 ETDRS letters). The non-inferiority test will be performed at week 52 using the PP population and with a non-inferiority margin of 10%. If the lower limit of 95.1% CI of difference in proportion of response (abicipar minus ranibizumab) is $\geq -10\%$, non-inferiority of abicipar to ranibizumab will be established.

[REDACTED]

[REDACTED]

The non-inferiority comparisons will also be performed in the ITT population as a sensitivity analysis to confirm the primary analysis.

Sensitivity analyses of handling missing data will be performed using multiple imputation.

Approval Date: 10-Apr-2018

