6.1 Study Treatment – Exposure and Administration

6.1.1 Exposure to Study Treatments

Exposure to study treatment will be evaluated by the number of study injections (including sham), the number of active study injections (excluding sham) and exposure days. Patients who have missed any study treatment(s) will be enumerated. Duration of treatment based on the days from the 1st to the last active study injections (excluding sham) will be calculated. Descriptive statistics will be tabulated for each treatment group using the safety population.

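### Does counting sham injections in the per-protocol compliance rule leave the primary non-inferiority test without an adequately dosed abicipar group?

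*SAP*

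**What the plan says.** SAP Section 2.1 defines the PP set by three criteria. The first requires that the patient "Received at least 9 study treatments (including sham) and attended at least 9 scheduled monthly visits during the first year", counted before the Week 52 visit. The second requires that the patient "Had not missed 3 or more consecutive study treatments (including sham) before the 9th study treatment". The third excludes major protocol deviations that affected efficacy before Week 52. Patients who discontinued as treatment failures without such a deviation are also included. The section gives its aim: "Primary considerations for PP definition include treatment compliance that would represent the intended regimen adequately". Membership is settled by masked data review, and "Detailed specification will be documented separately prior to the primary database lock".

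SAP Section 5.2.2 runs the primary non-inferiority test in the PP set. Protocol Section 7.3.1 adds: "The non-inferiority comparisons will also be performed in the ITT population as a sensitivity analysis to confirm the primary analysis". SAP Section 6.1.1 tabulates "the number of active study injections (excluding sham) and exposure days" by arm in the safety population. Protocol Section 1 gives the planned active dosing: "8 or 6 abicipar intravitreal injections in Year 1 for the 2Q8 and 2Q12 abicipar arms, respectively, versus 13 for the ranibizumab arm".

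**The concern.** Sham is given only to abicipar patients, at visits where no active dose is due. Of the 13 treatment visits from Week 0 to Week 48, 5 are sham in 2Q8 (13 − 8), 7 in 2Q12 (13 − 6) and none in rQ4. A threshold of 9 out of 13 that treats sham and active alike therefore guarantees 69% of active doses to the comparator, but only 50% and 33% to the two abicipar arms.

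That seems to conflict with the section's stated aim of representing the intended regimen. A 2Q12 patient who missed Weeks 12, 24, 36 and 48 would still meet the first two criteria with two active injections in the year. Protocol Section 5.6.1 also provides that "treatment dose may be temporarily held and the reason for dose holding will be recorded on the eCRF", so missed doses need not be haphazard. If such patients were common, the PP result would say less about abicipar as scheduled, and the PP set is where non-inferiority is decided. No analysis in the public text repeats the test among patients with a set share of their active doses.

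**Working it through.** **Inputs.** Four-weekly treatment visits from Week 0 to Week 48 make 13. The regimens in SAP Section 1.1 put active doses at:

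- 2Q12: Weeks 0, 4, 12, 24, 36, 48 (6)
- 2Q8: Weeks 0, 4, 8, 16, 24, 32, 40, 48 (8)
- rQ4: all 13 visits

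These reproduce the counts of 8, 6 and 13 in Protocol Section 1.

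**The floors.** Nine of 13 allows four misses. If all four fall on active visits, the remainders are 6 − 4 = 2, 8 − 4 = 4 and 13 − 4 = 9. The rule on consecutive misses does not raise these minima. With the baseline dose given, 2^12 = 4,096 patterns of received and missed visits are possible, and 714 meet criteria 1 and 2. Five of them reach 2/6 in 2Q12 and 35 reach 4/8 in 2Q8.

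**How often the floors occur.** The documents give no miss rates, so assume independent misses with probability m at each visit from Week 4 to Week 48. The share of patients meeting criteria 1 and 2 is 99.9%, 98.9% and 90.0% at m = 5%, 10% and 20%, the same in every arm. Every floor pattern has four misses in 12 visits. At m = 10%:

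- 2Q12 at 2/6: 5 × 0.1^4 × 0.9^8 / 0.989 = 0.02%, or 0.05 patients per 240
- 2Q8 at 4/8: 35 × 0.1^4 × 0.9^8 / 0.989 = 0.15%, or about 0.4 patients per 240

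**Average active dosing among qualifiers.**

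| m | 2Q12 | 2Q8 | rQ4 |
|---|---|---|---|
| 10% | 91.9% | 91.5% | 91.0% |
| 20% | 85.2% | 84.5% | 83.7% |

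A random miss hits active and sham visits in proportion, so the rule produces no average shortfall in the abicipar arms. They come out slightly higher because the baseline dose, taken as given, is a larger fraction of fewer doses.

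**Dependence on the cut-off.** Below two-thirds of active doses, the shares at m = 5%, 10% and 20% are 0.1%, 0.7% and 3.3% in 2Q12, 0.4%, 2.2% and 9.7% in 2Q8, and 0% in rQ4. The zero is built in, because two-thirds lies just under 9/13 = 69%. With a 75% cut-off at m = 20%, the shares are 9.7% in 2Q8, 12.6% in rQ4 and 21.6% in 2Q12. The 2Q8 comparison with rQ4 reverses; the 2Q12 comparison does not, because 4/6 = 67% falls short of 75%.

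**Early exit.** A patient who receives Weeks 0 to 32 and then leaves has nine treatments. The active doses among them are 4 of 6 (Weeks 0, 4, 12, 24), 6 of 8 (Weeks 0, 4, 8, 16, 24, 32) and 9 of 13, or 67%, 75% and 69%. For dropout, the only attrition the documents quantify (about 20% by Week 52), the common rule gives similar active dosing in each arm.

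**Misses that cluster in time.** Each of the five 2Q12 floor patterns consists of four isolated misses, all on active visits. If every miss belongs to a run of two or more, the minima rise to 4/6 in 2Q12 and 5/8 in 2Q8.

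**Effect on the endpoint.** Suppose patients below two-thirds had a stable-vision rate 30 points lower (an assumption). The arm's rate would fall by share × 30:

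- 2Q12: 0.03, 0.21 and 1.00 points at m = 5%, 10% and 20%
- 2Q8: 0.11, 0.65 and 2.92 points

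The margin is 10 points. The fall is in the abicipar rate, so it works against a claim of non-inferiority.

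**The case for a change.** The strongest counter-argument is that the aim in SAP Section 2.1 concerns the regimen, while its numerical criteria measure attendance. Neither the ITT comparison nor the exposure table gives a non-inferiority result by active-dose compliance. A supportive analysis in PP patients with, say, two-thirds of their active doses would cost one paragraph and one table. Misses may not be independent: dose holds after adverse events could fall on active visits, and the documents give no rates to exclude that.

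Part of this stands. The floors are real, no active-dose minimum appears in the public text, and the independence model is an assumption. But the proposed analysis would be harder to interpret than the one planned. At that cut-off it would remove abicipar patients only, on a variable observed after randomisation and with arm-specific thresholds. If under-dosed patients do worse, it would raise the abicipar rate and leave ranibizumab unchanged, which favours non-inferiority.

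Nor can its absence be established. SAP Section 5.3.1 refers to a Section 5.2.4.2 that the public text does not contain, Protocol Section 7.3.1 is partly redacted, and the detailed PP rules are in a separate specification. How missed active doses are classed under the third criterion is a detail that specification can hold.

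**Conclusion.** The concern does not hold. Counting sham with active treatments is a reasonable way to define a PP set that masked reviewers can settle with one rule for all arms. The third criterion and the separate specification remain available for patients whose missed doses matter.

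The unequal floors of 2/6, 4/8 and 9/13 are arithmetically right but describe rare patterns. Average active dosing among qualifiers differs by about 1 point between arms at 10% misses and 1.5 points at 20%, with abicipar slightly ahead. Under the assumed 30-point deficit, the abicipar rate would shift by at most 0.7 points at misses of 5% to 10% and 2.9 points at 20%, in the direction that makes non-inferiority harder to show. An extra supportive table would be a matter of preference and would correct no stated rule or result.

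This rests on independent misses after a baseline dose that was given, and on an assumed deficit. Treatment failures enter the PP set under their own provision and are outside these counts. The SAP is labelled 150998-005 and the protocol 150998-006, but their regimens agree and either gives the same dose counts.

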2.2 Handling Mis-randomization and Mis-stratification

In the event of mis-stratification that resulted in randomization under the wrong stratum, all PP analyses will be based on the actual stratum to which the patient belongs. ITT analysis that uses the randomization stratification factor(s) will be based on the stratum as randomized for the primary efficacy analysis and the actual stratum to which the patient belongs for other analyses such as model-based approaches.

2.3 Analysis Visit Windows

Analysis visit windows are defined according to study days, which are defined in Table 1.

Visit windows defined in Table 1 will be applied to all by-visit analyses of efficacy and safety variables. Out-of-window visits (including the exit visit) and unscheduled visits will be reassigned to the visit that the actual study days fall within.

In cases where multiple visits occurred within a single visit window, which resulted in multiple data points for the same window, the last visit with non-missing data will be used for analysis.

Visit	Target Day of Visit	Analysis Visit Window (Study Days)
Baseline (Day 1)	1	≤ 1
Week 4	28	2-42
Week 8	56	43-70
Week 12	84	71-98
Week 16	112	99-126
Week 20	140	127-154
Week 24	168	155-182
Week 28	196	183-210
Week 32	224	211-238
Week 36	252	239-266
Week 40	280	267-294
Week 44	308	295-322
Week 48	336	323-350
Week 52	364	351-378
Week 56	392	379-406
Week 60	420	407-434
Week 64	448	435-462
Week 68	476	463-490
Week 72	504	491-518
Week 76	532	519-546
Week 80	560	547-574
Week 84	588	575-602
Week 88	616	603-630
Week 92	644	631-658
Week 96	672	659-686
Week 100	700	687-714
Week 104	728	715-742

Table 1	Definitions for A	Analysis Visit	Windows
	Deminitions for F	Allaly 515 V 1510	, williuows

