8.5 Unscheduled Visits

Additional examinations may be performed as necessary to ensure the safety and well-being of patients during the study. The eCRFs should be completed for each unscheduled visit.

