1.1 Primary Study Objectives and Design

The study objectives are to assess the safety and efficacy of abicipar compared with ranibizumab in treatment-naïve patients with nAMD.

The clinical hypotheses are:

- Multiple intravitreal injections of 2 mg abicipar have an acceptable safety profile in treatment-naïve patients with nAMD
- The efficacy of at least 1 of the 2 abicipar regimens is noninferior to that of monthly ranibizumab intravitreal injections as assessed by the proportion of patients with stable vision at Week 52

This is a multicenter, double-masked, randomized, 104-week, parallel-group, activecontrolled study to evaluate the safety and efficacy of abicipar in treatment-naïve patients with nAMD. Approximately 900 patients will be randomized by region with a 1:1:1 allocation ratio to receive one of the following three treatments:

• Treatment group 2Q8: 2 mg abicipar administered at baseline (Day 1) and Weeks 4 and 8, followed by doses at 8-week intervals through Week 96

- Treatment group 2Q12: 2 mg abicipar administered at baseline (Day 1), and Weeks 4 and 12, followed by doses at 12-week intervals through Week 96
- Treatment group rQ4: 0.5 mg ranibizumab administered every 4 weeks from baseline (Day 1) through Week 96

Regions are defined primarily based on geographical locations (eg, North America, EAME [Europe, Africa, and Middle East], Asia Pacific, and Latin America). For randomization purposes, some regions are combined and the following 3 regions are used: North America, Asia, and the rest of the world. The defined 3 regions for randomization will be used for statistical analysis. Within each region, randomization to treatment groups will be stratified by baseline value for best-corrected visual acuity (BCVA \leq 55 versus > 55 ETDRS letters), central retinal thickness (CRT \leq 400 versus > 400 microns), and lesion type of choroidal neovascularization (predominantly classic versus minimally classic or occult) in the study eye.

The study design including treatment and visit schedules is shown in Figure 1 below.

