5.2 Primary Efficacy Analyses

The primary efficacy endpoint is the proportion of patients with stable vision at Week 52, defined as vision loss of fewer than 15 letters in BCVA from baseline. Patients who escaped to standard of care by meeting the protocol criteria will be set to failures for the primary endpoint of stable vision at Week 52. Confirmation for meeting the protocol criteria is based on the marked reasons captured on the Standard of Care eCRF, which states: "Loss of \geq 30 letters in BCVA from baseline (in any post-baseline visit), and persistent fluid (subretinal and intraretinal) by OCT, judged to be the cause of the BCVA loss (not explained by reasons other than the progression of neovascular AMD)."

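### A BCVA recorded after the scheduled Week 52 visit, up to Day 378, replaces the pre-injection Week 52 value, and the injection in between is active in rQ4 but sham in both abicipar arms

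*SAP*

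**What the plan says.** SAP 2.3 sets the scope widely: "Visit windows defined in Table 1 will be applied to all by-visit analyses of efficacy and safety variables". Visits off schedule are placed by date: "Out-of-window visits (including the exit visit) and unscheduled visits will be reassigned to the visit that the actual study days fall within". If this leaves more than one visit in a window, "the last visit with non-missing data will be used for analysis". Neither the scheduled visit nor the visit nearest the target day is preferred. In SAP Table 1 the Week 52 target is Day 364 and the window is Days 351 to 378.

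The primary endpoint depends on that window. SAP 5.2 states: "The primary efficacy endpoint is the proportion of patients with stable vision at Week 52". The readable text of SAP 5.1, 5.2 and 5.2.2 makes no exception to the window rule. Two provisions limit its reach. SAP 5.1 drops efficacy data after a first non-study anti-VEGF treatment in the study eye. SAP 5.2 counts patients who escape by the protocol criteria as failures.

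SAP 1.1 gives 2Q8 as "2 mg abicipar administered at baseline (Day 1) and Weeks 4 and 8, followed by doses at 8-week intervals through Week 96" and 2Q12 as "2 mg abicipar administered at baseline (Day 1), and Weeks 4 and 12, followed by doses at 12-week intervals through Week 96". The rQ4 arm is treated every 4 weeks through Week 96. Protocol 5.6 gives abicipar patients a sham at visits without a scheduled dose. Protocol 6.4.2.1 puts BCVA before any contact with the study eye. Protocol 8.5 provides for unscheduled visits: "Additional examinations may be performed as necessary to ensure the safety and well-being of patients during the study".

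**The concern.** A patient seen on time has a Week 52 BCVA measured before that visit's injection. If the same patient returns a few days later and BCVA is recorded again, the rule discards the scheduled value and analyses the later one. Two features make this more than a formality. The later value follows an injection that is active in one arm and sham in the other two. And an unscheduled return is likely to be prompted by a problem, so the patients whose values are replaced are not a random subset.

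At stake is whether the Week 52 endpoint measures the same thing in each arm, namely vision before the Week 52 treatment. The rule covers all by-visit efficacy analyses, so it also reaches the 15-letter gain (SAP 5.3.3), the Week 52 value in the MMRM (SAP 5.3.1), and the ITT versions. Multiple imputation does not address it, because no value is missing.

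**Working it through.** **1. Dose calendar from SAP 1.1.**
- 2Q8: Weeks 0, 4, 8, 16, 24, 32, 40, 48, 56 and so on. Week 52 is sham.
- 2Q12: Weeks 0, 4, 12, 24, 36, 48, 60 and so on. Week 52 is sham.
- rQ4: every 4 weeks. Week 52 is active.

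Active doses before Week 52 number 8, 6 and 13, which matches Protocol 1. Both abicipar arms have an active dose at Week 48.

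**2. Exposed days.** SAP 2.4 defines study day as the date difference plus 1, so a visit exactly 52 weeks after the first treatment is Day 52 × 7 + 1 = 365. The window closes at Day 378, leaving 378 − 365 = 13 later days on which a recorded BCVA displaces the scheduled one. A Week 56 visit held at least 392 − 378 = 14 days before its target does the same.

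**3. Comparison with the SAP's other rules.** For baseline, SAP 2.4 turns to screening or unscheduled visits only when the baseline visit lacks the data, so there the scheduled visit takes precedence. For adverse events, SAP 6.2 closes the Week 52 period at the Week 52 visit date for patients who attended it. A complication starting on Day 370 after a Day 365 visit is thus outside the Week 52 adverse-event tables, yet its BCVA can enter the primary endpoint.

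**4. The plan's own sample size.** With 90% in both groups, margin 10 points, two-sided alpha 0.05 and 95% power: n = (1.960 + 1.645)² × (0.09 + 0.09) / 0.10² ≈ 234 per group, against 240 stated. At 240, SE = √(0.18/240) = 0.0274 and power = Φ(0.10/0.0274 − z), which is 95.5% at alpha 0.05 and 95.4% at 0.049. Allowing 20% dropout, 720/0.80 = 900. The stated figures reproduce.

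**5. Sensitivity to replacement (assumed; the documents give no frequency).** Let f be the *net* share of rQ4 patients whose classification moves from stable to not stable. Negative f means net improvement. The abicipar arm is held fixed, n = 240 per arm, alpha = 0.049 (z = 1.969), with an unstratified normal approximation.
- Type I error, true rates 80% and 90%: Φ((0.80 − (0.90 − f) + 0.10)/SE − 1.969).
- Power, true rates 90% and 90%: the same with 0.90 in place of 0.80.

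Example, f = 1%: SE = √((0.89 × 0.11 + 0.80 × 0.20)/240) = 0.0328, and Φ(0.01/0.0328 − 1.969) = 0.048.

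| Net f | Patients of 240 | One-sided type I error | Power |
|---|---|---|---|
| +2% | 4.8 | 0.086 | 98.7% |
| +1% | 2.4 | 0.048 | 97.5% |
| +0.5% | 1.2 | 0.035 | 96.6% |
| 0 | 0 | 0.0245 | 95.4% |
| −0.5% | 1.2 | 0.017 | 93.8% |
| −1% | 2.4 | 0.011 | 91.8% |
| −2% | 4.8 | 0.005 | 86.3% |

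If both arms shift by the same net share, the difference is unchanged: (0.80 − f) − (0.90 − f) = −0.10. Only an imbalance between arms matters.

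**The case against.** A reader might infer that the rule favours abicipar, on the reasoning that only rQ4 patients have just had a real injection and so only they can suffer a drug-related complication in this window. The documents do not support that. Both abicipar arms receive active drug at Week 48, and the Week 52 window opens on Day 351, the day after the Week 48 window closes. Protocol 9.3 requires serious adverse events to be reported for at least 16 weeks after the last dose, so the plan does not treat drug effects as ending within four weeks. Intraocular inflammation is an event of special interest in SAP 6.2.1. Problem visits in the abicipar arms fall under the same rule and would lower the abicipar rate. The extra ranibizumab dose could also improve rQ4 vision at a later visit.

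Other points also stand in part:
- Protocol 8.5 calls for examinations as needed and does not require BCVA at an unscheduled visit. Without a recorded BCVA there is no replacement.
- Changing a classification takes a large shift. A patient 8 letters above baseline at the scheduled visit must lose 8 + 15 = 23 letters to count as not stable.
- The rule is prespecified, is the same for all arms, and is applied to BCVA collected by masked assessors. It is not an error in itself.
- SAP 5.3.1 cites a Section 5.2.4.2 that cannot be read, and much of the protocol's visit schedule is redacted, so an exception may exist there.

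These points remove the directional claim and limit the size. They give no reason to discard a valid scheduled pre-injection value in favour of a later one.

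**Conclusion.** The concern holds as a question of what the Week 52 value measures. On the readable text, a BCVA recorded after the scheduled Week 52 visit and by Day 378 replaces the scheduled value, unless non-study anti-VEGF treatment came first or the patient already counts as a failure through escape. The replacement follows an injection that differs by arm, and it is unlikely to be random.

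Neither direction nor size can be taken from the documents. The table shows only that the non-inferiority test is sensitive to a net imbalance of a few patients, in either direction. It is not an estimate of what will happen, and it sets abicipar replacements to zero. Most patients will have a single visit in the window, so the effect is probably small. The point is a near-costless improvement to the plan and does not by itself put the primary analysis in doubt.

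The conclusion assumes no exception in the unreadable text. The SAP is labelled for Study 150998-005 and the protocol for 150998-006; their regimens agree, and the conclusion takes the SAP's rule as applying to this protocol.

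**What to change.** In SAP 2.3, for efficacy analyses, replace the last-visit rule with:

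*If the scheduled visit falls within the window and has a non-missing assessment, its pre-injection assessment is used; otherwise the non-missing assessment closest to the target day is used, with preference to assessments made before that visit's injection.*

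The specification should make clear that *the scheduled visit* means the nominal visit for that window, so that an early Week 56 visit cannot displace Week 52. It should also say that *injection* includes sham, so that the rule runs identically in all arms and can be programmed masked. The second clause covers a scheduled visit that is in window but has no BCVA. All unscheduled values stay in the safety analyses.

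The cost is one sentence and a small programming change, with no effect on sample size or data collection. It should be made before the Week 52 unmasking. A masked count of patients with more than one BCVA in Days 351 to 378 would show how many values the choice of rule can affect.
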